7.3 Statistical Methods

In the following analyses, primary outcome measures will include the “per protocol” population. The secondary measures will include the “intent to treat” population.

Primary analysis: Paired t tests will be conducted between the lowest score from the post-treatment assessments and the baseline symptom levels to assess the maximum effect of ketamine infusion on symptoms for each person.

Secondary Analyses:

1. We will calculate the time to relapse for each participant.
2. Biological Mechanisms:
 - a. Neuroimaging data: Paired t tests will be conducted to evaluate pre- and post ketamine treatment changes in measures of brain functional activation, connectivity, white matter microstructure and brain metabolite concentrations. These preliminary data will be used to identify responsive measures and estimate sample sizes that would be needed to use these measures as endpoints in future studies.
 - b. Bimolecular studies to examine mechanisms of cellular resilience (insulin challenge, cytokine testing, gene expression) will be conducted to evaluate change in these pathways before and after ketamine. Analyses will be conducted by [name] at Mayo Clinic. Peripheral blood mononuclear cells (PBMCs) will be isolated from whole blood and divided into two groups. The first group will not receive any treatment. RNA will be extracted and whole genome microarray will be performed using illumina's genome-wide gene expression arrays. Differential pre- versus post-ketamine mRNA levels will be quantified and bioinformatics pathway analysis will be used to identify key differences in molecular responses to ketamine. A second subset of PBMCs will be cultured and cryopreserved. Once all samples are collected cells will be immortalized to ensure sufficient tissue availability. The following two separate analyses will then be performed:

CONFIDENTIAL

- i. Group 1 PBMCs will be stimulated with insulin and intracellular Akt, mTOR, and GSK3 gene and protein levels will be quantified following 0, 5, 15, and 30 minutes of stimulation. This signaling pathway is implicated in mediating the antidepressant response to ketamine. Western blot and rtPCR techniques will be used to quantify protein and gene expression, respectively;
- ii. Group 2 PBMCs will be immortalized and undergo inflammatory challenge via stimulation with phytohemagglutinin. Levels of cytokines and kynurenines will be measured in the culture medium 1, 3 and 24 hours post-stimulation. ELISA kits will be used to quantify proinflammatory cytokine levels.

Outcomes of each assay will be correlated with patient response profile. All tissue will be destroyed upon completion of the study.

Interim Analysis: The above analyses will be conducted on data from the first ten subjects to ensure that there is preliminary support for the proposed hypotheses.

8 Safety and Adverse Events

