| PHA | Phytohemagglutinin |
| PHI | Protected Health Information |
| PI | Principal Investigator |
| POMS-A | Profile of Mood States – Adolescent |
| REPA | Report of External Professional Activities |

CONFIDENTIAL

| | |
|-------|--|
| SAE | Serious Adverse Event |
| SHAPS | Snaith-Hamilton Pleasure Scale |
| TRD | Treatment-Resistant Depression |
| TEPS | Temporal Experience of Pleasure Scale |
| UTox | Urine Toxicology Screen |
| VA | Veterans' Affairs |
| WASI | Weschler Abbreviated Scale of Intelligence |

Study Summary

| | |
|---------------------------------------|--|
| Title | Open-label intravenous subanesthetic ketamine for adolescents with treatment-resistant depression |
| Protocol Number | CTSI 22225 |
| Phase | 2 |
| Methodology | Single group open-label pilot study |
| Study Duration | 2 years |
| Study Center(s) | University of Minnesota |
| Objectives | To determine the efficacy of repeated-dose subanesthetic IV ketamine among adolescent patients with treatment resistant depression. |
| Number of Subjects | 20 |
| Diagnosis and Main Inclusion Criteria | Male and female adolescents aged 12 to 18 with the presence of recurrent major depressive disorder without psychotic features. |
| Study Product, Dose, Route, Regimen | IV infusions of 0.5mg/kg of Ketamine hydrochloride over a 40-minute infusion period. Participants will receive a total of 6 doses over a 2-week period. |
| Duration of administration | 2 weeks |
| Reference therapy | Not applicable. |
| Statistical Methodology | 
The maximum effect of the ketamine infusions on symptoms for each participant will be assessed by conducting paired t tests between the lowest score from the post-treatment assessments and the baseline symptoms levels.
 
The time to relapse for each participant will be calculated and an average relapse time for the group will be reported.
 
Exploratory analysis will be done on changes in brain function, connectivity and chemistry, as well as in peripheral blood biomarkers.
 |

1 Introduction

This document is a protocol for a human research study. This study will be conducted according to US and international standards of Good Clinical Practice (FDA Title 21 part 312 and International Conference on Harmonisation guidelines), applicable government regulations and Institutional research policies and procedures.

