To determine the efficacy of repeated-dose subanesthetic IV ketamine among adolescent patients with treatment resistant depression (TRD). *Hypothesis:* Based on previous results in adults with TRD, we predict that response rates will improve over the course of six treatments of ketamine.

Secondary Objectives:

To explore the durability of antidepressant response to repeated dose of IV ketamine in a 6-week observational period. *Hypothesis:* Based on the inherent neuroplasticity in adolescence due to ongoing neurodevelopment, adolescents may show a more durable clinical response than has been seen in adults.

To study the neurobiological mechanisms of response to ketamine. We will explore how clinical improvement relates to change in brain function, brain connectivity, brain chemistry, and in peripheral blood biomarkers of neuroplasticity and cellular resilience.

3 Study Design

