3.1 General Design

This is a single-group (n=20) open-label pilot study of 6 doses of IV ketamine, 3 doses per week over a 2-week period, followed by a 4-week post-treatment observational period. Symptom levels will be assessed prior to infusion, directly after infusion, 1 and 2 hours after infusion. We will also assess symptoms weekly for 6 weeks after the last ketamine infusion. A study goal is to identify neurobiological biomarkers of treatment response using neuroimaging and blood studies.

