3.2 Primary Study Endpoints

The primary outcome measure is response status as defined by Children's Depression Rating Scale (CDRS) (Poznanski, 1985) Responders will be defined as having a significant reduction in their CDRS score ($\geq 50\%$) whereas non-responders will be defined as subjects whose scores do not show such a significant reduction or whose score increase. The percent change will be calculated by the formula below (Tao, 2009):

$$(\text{Baseline CDRS} - \text{Exit CDRS}) / (\text{Baseline CDRS} - 17)$$

Baseline CDRS: CDRS score obtained on Visit 1 – Baseline Assessment (Section 6.1)
Exit CDRS: the latest CDRS score obtained on Visit 10 - Clinical Assessment (Section 6.6) or Visit 11-16 – Follow-up Period (Section 6.7)

CONFIDENTIAL

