4.1 Inclusion Criteria

Patients will be eligible to participate in the study if all of the following conditions exist:

- 1) Willing and able to provide informed consent and assent.
- 2) Male and female adolescents aged 12 to 18 years.
- 3) Presence of recurrent MDD confirmed by the K-SADS-PL (Kaufman et al., 1997).
- 4) Current depression severity measured by the Children's Depression Rating Scale (CDRS) (Poznanski, 1985) raw score greater than or equal to 36 at screening and the day ketamine is due to be received for the first time.
- 5) Current depressive episode resistant to treatment, defined as failure to achieve remission (elimination of symptoms and restoration of pre-morbid psychosocial functioning) from at least 2 antidepressant trials. Systematic evaluation of previous antidepressant trials will be assessed by using the Antidepressant Treatment History Form (Sackeim, 2001).
- 6) If present, current antidepressant medication treatment must be dose stable for at least 2 months prior to beginning the study*
- 7) Participants should have a medical history and physical examination in the 30 days prior to initiating the ketamine infusions.

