6.7 Visits 11-16 – Follow-up period

All participants will be asked to speak with the research team for weekly follow-up visits for 6 weeks. Participants will continue to take medications as prescribed by their doctor. At each of these visits, participants will be asked about any medication changes and will complete the same assessments as administered in visit 10 (MADRS, CADSS, POMS-A, SHAPS, TEPS, BDI-II, CGI, CDRS and BPRS).

All participants will be asked to participate in the 6 weekly follow-up visits, regardless of response.

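### The primary test compares each participant's lowest post-treatment score with one baseline score, so it rejects in most trials with no true change, and the declared responder endpoint has no analysis

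*Combined protocol and SAP*

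**What the plan says.** Section 7.3 gives the primary analysis as: "Paired t tests will be conducted between the lowest score from the post-treatment assessments and the baseline symptom levels". The Study Summary repeats it, again using "the lowest score from the post-treatment assessments and the baseline symptoms levels". Both describe this as capturing each person's largest effect. Neither names the scale or says which visits count as post-treatment.

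Section 3.2 declares something else: "The primary outcome measure is response status as defined by" the CDRS. A responder has a reduction of at least 50%, calculated as (baseline − exit) / (baseline − 17). Baseline is the Visit 1 score, and the exit score is "the latest CDRS score obtained on Visit 10" or at Visits 11–16.

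The primary hypothesis in Section 2 concerns response over time: "we predict that response rates will improve over the course of six treatments of ketamine".

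On scheduling, Section 6.6 lists the CDRS at Visit 10. Section 6.7 says that participants at the six weekly follow-ups "will complete the same assessments as administered in visit 10", and names the CDRS among them. Sections 6.3 and 6.4 list no CDRS at the infusion visits, although Section 4.1 requires a "raw score greater than or equal to 36 at screening and the day ketamine is due to be received for the first time". The end of Section 7.3 applies the same analyses to the first ten subjects as an interim check.

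**The concern.** A paired t test asks whether the mean difference is zero. If one side of the pair is the smallest of several scores and the other is a single score, the expected difference is below zero whenever scores fluctuate, drug or no drug. The null hypothesis is false by construction, and every excess rejection points towards benefit.

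The primary p-value would then say almost nothing about efficacy, and the reported improvement would be inflated. The interim on ten subjects would inherit the same fault. Meanwhile the declared endpoint would have no prespecified result. Section 7 mentions response only as something to correlate with the laboratory assays. The hypothesis about response over six infusions has no analysis either, and no CDRS is listed at the visits where it would be needed.

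**Working it through.** The plan states no alpha, power, effect size or standard deviation, so there is no figure of its own to reproduce. The check is the false-positive rate of the test as written.

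**Inputs from the protocol**
- n = 20 (Section 3.1); interim n = 10 (Section 7.3).
- Post-treatment CDRS scores: 1 (Visit 10) + 6 (Visits 11–16) = 7. One clause in Section 3.1 has the infusions "followed by a 4-week post-treatment observational period", which would give about 1 + 4 = 5. The same section and Sections 5.5, 6.7 and 6.8 say six weeks.

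**Assumptions**
- Two-sided 5% level; no true change; normal scores with equal variance at all visits.
- Week-to-week (AR(1)) error correlation from 0 to 0.9.
- First post-treatment score three weeks after Visit 1.

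**Analytic case.** Let d = min(Y1,…,Y7) − Y0, with equal correlation ρ between all scores. For seven independent standard normal scores the minimum has mean −1.351 and variance 0.392. The factor √(1 − ρ) multiplies both the mean and the SD of d and cancels, so for any ρ:

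standardised effect = 1.351 / √(1 + 0.392) = 1.145.

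The noncentrality is 1.145 × √20 = 5.12 for n = 20 and 1.145 × √10 = 3.62 for n = 10. The noncentral t distribution then gives rejection rates of 99.8% and about 90%.

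**Simulation, AR(1) errors, 20,000 trials per cell**

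| Weekly correlation | 7 scores, n=20 | 7 scores, n=10 | 5 scores, n=20 | 5 scores, n=10 |
|---|---|---|---|---|
| 0 | 99.9% | 89.7% | 98.6% | 77.6% |
| 0.5 | 98.2% | 77.3% | 91.5% | 59.0% |
| 0.7 | 94.9% | 66.3% | 82.4% | 48.0% |
| 0.9 | 86.5% | 52.1% | 69.1% | 36.5% |

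One fixed post-treatment visit gives about 5% throughout.

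**Spurious mean drop.** With seven scores it is 0.62 (correlation 0.9) to 1.35 (correlation 0) within-person SDs. For an assumed within-person SD of 5 to 8 CDRS points, that is 0.62 × 5 = 3.1 to 1.35 × 8 = 10.8 points. With five scores it is 0.48 × 5 = 2.4 to 1.17 × 8 = 9.4 points.

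**Harsher settings**
- With seven scores and n = 20, a pure random walk still gives 79% (43% at n = 10).
- With equal correlation and n = 20, two scores per person give about 46% and three give about 82%. The result therefore depends on how many scores count, which the plan does not define.

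**Regression to the mean.** The entry cut of CDRS ≥ 36 biases even a fixed visit. Assume a pre-selection mean of 36 to 55, a between-person SD of 8 to 10 and a within-person SD of 5 to 8, with selection at Visit 1 only. The fixed-visit test then rejects in about 4% to 44% of null trials, with a drop of 0 to 4.4 points. If the cut is applied twice, as Section 4.1 requires (second score assumed one week later), the upper end falls to about 30%. In the Visit 1 runs the lowest-score test rejects in 88% to 100%.

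**Declared endpoint.** Sections 3.2 and 7.3 differ in the quantity (response status against mean change) and in the score (latest against lowest). Section 7 contains no responder proportion, interval, test or reference rate.

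**The case against.** - **The label is open and the trial is a pilot.** Section 7.3 says plainly that it seeks the largest effect, and Section 5.2 foresees a placebo-controlled trial afterwards. The interim carries no stopping or continuation rule. These points limit the consequences but do not repair the test: it is called the primary analysis, the objective in Section 2 is efficacy, and the results are meant to support the next trial.
- **Seven evenly spaced scores at n = 20 is an ideal.** Visits 10 and 11 may be only days apart, and the primary population is those who complete six infusions. With those visits two days apart, the lowest rate at n = 20 is about 83% rather than 86%. With 15 completers it is about 70%. The interim floor drops slightly below one half. These points stand, but the conclusion at the final analysis does not change.
- **The five-score case rests on one clause.** That is fair; seven is the main case.
- **Response can be computed from Section 3.2.** True: the formula and threshold are complete for each participant. What is missing is any stated group estimate or interval, and a single agreed score.
- **Without a control, no p-value here establishes efficacy.** Also true, and regression to the mean remains at a fixed visit. The bias from taking the lowest score is additional and avoidable.

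**Conclusion.** The concern holds and should be fixed before analysis. With the scheduled seven CDRS scores and 20 participants, the primary test rejects with no true change in about 86% to 99.9% of trials under AR(1) correlation of 0 to 0.9, against about 5% for one fixed visit. At the ten-subject interim the range is about 52% to 90%. These rates assume a two-sided 5% level, normal scores, near-complete follow-up and the CDRS as the scale. They would fall below one half at the final analysis only if very few scores per person counted, about two. That the responder endpoint has no analysis and that Sections 3.2 and 7.3 use different scores follow from the text and need no assumption.

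**What to change.** Amend the Study Summary and Sections 3.2 and 7.3:

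1. Name one post-treatment visit for the exit CDRS, for example Visit 10, and state that it replaces the latest available score.
2. Make the primary analysis the responder proportion at that visit, using the Section 3.2 formula, with an exact 95% confidence interval. State how a missing score counts, for example as non-response. Report the same figure for everyone who received at least one dose, since the completer set leaves out early dropouts.
3. Run the paired t test from Visit 1 to that same visit, naming the CDRS. A prespecified repeated-measures model is an alternative for the mean change.
4. Report the lowest score descriptively only.
5. Use the fixed-visit measures at the interim.
6. For the Section 2 hypothesis, describe MADRS response by infusion number. The MADRS is already scheduled before and two hours after each infusion. Choose one of those times in advance, and complete the response definition in Section 3.3, which gives 50% without saying of what. That section also notes that the scale is not validated in adolescents.
7. Reconcile the first-infusion-day CDRS in Section 4.1 with the list in Section 6.3.
8. State that regression to the mean and the absence of a control remain, so the findings are preliminary.

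The cost is wording; the proposed analyses need no new data. The reported effect will be smaller than the best-score figure, and a missed fixed visit loses information. The responder interval will be wide: 5/20 gives 8.7% to 49.1%, 10/20 gives 27.2% to 72.8%, and 15/20 gives 50.9% to 91.3%.

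### The imaging objective asks how brain change relates to clinical improvement, but the only imaging analysis planned in Section 7.3 (item 2a) is a pre/post paired t test with no clinical variable in it

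*Combined protocol and SAP*

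**What the plan says.** Section 2 words the mechanism objective as an association: "We will explore how clinical improvement relates to change in brain function, brain connectivity, brain chemistry, and in peripheral blood biomarkers". Section 3.1 restates the aim: "A study goal is to identify neurobiological biomarkers of treatment response using neuroimaging and blood studies".

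For imaging, Section 7.3 (item 2a) specifies one analysis: "Paired t tests will be conducted to evaluate pre- and post ketamine treatment changes in measures of brain functional activation", extended in the same sentence to connectivity, white matter microstructure and brain metabolites. Its stated use follows: "These preliminary data will be used to identify responsive measures and estimate sample sizes that would be needed to use these measures as endpoints". The Study Summary likewise speaks of change alone: "Exploratory analysis will be done on changes in brain function, connectivity and chemistry, as well as in peripheral blood biomarkers".

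The only association analysis in the plan closes item 2b of Section 7.3: "Outcomes of each assay will be correlated with patient response profile". It follows the blood-cell stimulation and cytokine work and is followed by a sentence on destroying tissue.

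**The concern.** The objective concerns the joint behaviour of two quantities within a participant: change in a brain measure and change in depression score. The planned test uses only the first. It can find that a measure shifts on average in everyone, improved or not, and it can miss a measure that rises in those who improve and falls in those who do not. Neither result bears on the question in Section 2.

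The objective names brain measures and blood biomarkers in one sentence, yet the link to response is planned for blood alone. If an imaging-response analysis is added only after the data are in, the measures, the clinical score and the time point would all be open to choice with results in hand. In a 20-participant pilot meant to inform later studies, that would weaken whatever is reported.

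**Working it through.** **1. Setting the sections side by side.**

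- Section 2: the target is a relation between clinical improvement and brain change.
- Section 3.1: the target is biomarkers of treatment response.
- Section 7.3 (2a): the test is mean post-minus-pre change against zero, with no clinical variable.
- Section 7.3 (end of 2b): correlation with response, for assays.
- No section plans a correlation, regression or responder/non-responder comparison for the MRI measures.

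**2. Does the paired t test carry any information on the association?** The statistic is t = mean(D) / (SD(D)/√n), where D is imaging change. Clinical change does not appear. A simulation makes this concrete (assumptions: bivariate normal changes, n = 20, two-sided 5% level, 20,000 replicates).

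| Mean imaging change | True correlation with improvement | Paired t rejects | Correlation test rejects |
|---|---|---|---|
| 0 | 0.7 | 4.9% | 95.4% |
| 0.8 SD | 0 | 92.4% | 4.9% |
| 0.8 SD | 0.7 | 92.5% | 96.0% |
| 0 | 0 | 5.2% | 4.8% |

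The paired t rejection rate follows the mean change and does not respond to the correlation.

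**3. What an association analysis could deliver.** Section 3.1 gives the size: "This is a single-group (n=20) open-label pilot study of 6 doses of IV ketamine". Section 7.1 gives no alpha, power or effect size, so there is no planned figure to reproduce. The 5% two-sided level and the smaller sample sizes below are assumptions.

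Interval for an observed r of 0.5: tanh(atanh(0.5) ± 1.96/√(n − 3)), with atanh(0.5) = 0.549.

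- n = 20: 0.549 ± 0.475, giving 0.07 to 0.77.
- n = 16: 0.549 ± 0.544, giving 0.01 to 0.80.
- n = 15: 0.549 ± 0.566, giving −0.02 to 0.81.

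Smallest correlation reaching p < 0.05 at n = 20: r = t/√(df + t²).

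- Simple correlation, 18 df: 2.101/√(18 + 4.414) = 0.444.
- Adjusted for the pre-treatment imaging value, 17 df: 2.110/√(17 + 4.451) = 0.456.

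Smallest true correlation detectable with an assumed 80% power, for one measure: tanh((1.960 + 0.842)/√(n − 3)), which is 0.59 at n = 20 and 0.65 at n = 16.

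**4. How many scan pairs?** Twenty is a ceiling. Section 6.2 allows the MRI to be waived for an inpatient when a pass is judged unsafe, and Section 5.5 ends participation for non-compliance. The documents give no expected number of lost pairs.

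**5. Which clinical score?** Sections 6.5 and 6.6 place the second scan and the Visit 10 CDRS-R within one week of the last infusion. Section 3.2 defines Exit CDRS as the latest score from Visit 10 or Visits 11 to 16, so it may come from any of six later weekly visits. For relating improvement to the scan, Visit 10 is the closer match.

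**6. Are the data there?** Section 6.2 lists two functional scans, a T1 image and diffusion tensor imaging, and Section 6.5 makes the second scan identical. These serve the activation, connectivity and white-matter measures. No spectroscopy sequence is listed, so the brain-chemistry measure in Sections 2 and 7.3 has no described data source, either for the planned t test or for a regression.

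**The case against.** The strongest defence is that this is a secondary objective, worded as exploration, carrying no hypothesis, in a pilot. No primary conclusion or safety matter depends on it, and nothing in the plan forbids an exploratory correlation. For the purpose item 2a states, finding measures that respond and sizing later studies, a paired pre/post estimate is suitable. All of this stands. It limits the severity but leaves the Section 2 question without a planned analysis.

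It might be argued that the correlation sentence at the end of item 2b also covers imaging, since it stands as its own paragraph. Its reference to assays and the tissue sentence that follows tie it to the blood work.

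Three stronger readings are tempting and are not supported:

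- A reader might infer that measures without a mean change will be thrown out. Section 7.3 states no such rule.
- A reader might infer that the missing control group is the defect here and that a regression would cure it. Section 5.2 acknowledges the lack of placebo and defers to a later randomised trial. A change-on-change association in one arm is open to the same influences, since spontaneous improvement could drive both quantities.
- A reader might infer that every imaging measure can be analysed from data already planned. That fails for brain chemistry.

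Testing every measure for association with so few participants would also invite chance findings, so the remedy needs a limit on the number of measures.

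**Conclusion.** The mismatch holds and is structural: the imaging part of the mechanism objective is an association, and the imaging analysis contains no clinical variable. It does not depend on a power figure. It is confined to imaging, because the blood part has a planned correlation. The paired t tests are not wrong; they answer a different question.

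An added analysis would be imprecise: a 95% CI of 0.07 to 0.77 around an observed correlation of 0.5 with all 20 pairs, 0.01 to 0.80 with an assumed 16, and a critical partial correlation of about 0.46 in the adjusted model at n = 20. These figures assume a two-sided 5% level and a single measure without multiplicity adjustment. The output would be an estimate of association and would not separate ketamine from time or concomitant treatment. Severity is minor to moderate.

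**What to change.** Add to Section 7.3 (item 2a):

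- A small set of imaging measures named in advance (region or connection, and modality).
- For each, a linear regression of post-minus-pre change on CDRS percent change, using the Section 3.2 formula with the Visit 10 score in place of Exit CDRS, adjusted for the pre-treatment imaging value. State openly that this differs from the latest-score rule in Section 3.2, and why.
- The slope and a rank correlation, each with a 95% CI and the number of scan pairs, labelled exploratory. State how many measures were tested, or control multiplicity across them.
- A sentence saying that the result is an association within a single arm.

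Keep the paired t tests as description, and consider both results when choosing measures for later studies.

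For the functional, connectivity and diffusion measures the cost is a paragraph of plan and a little analysis on scans and ratings already scheduled. For brain chemistry, first reconcile Sections 2 and 7.3 with the scan list in Section 6.2: either describe the acquisition or remove the component.

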7.1 Sample Size Determination

In view of the lack of any reports on ketamine in adolescent depression, the study sample was based on published studies in adult depression.

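### The ten-subject check for preliminary support relies on a lowest-score test that often shows improvement when nothing has changed

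*Combined protocol and SAP*

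**What the plan says.** Section 3.1 gives the size and design: "This is a single-group (n=20) open-label pilot study of 6 doses of IV ketamine". Section 7.1 gives no effect size, standard deviation, significance level or power, only that "the study sample was based on published studies in adult depression".

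In Section 7.3 the primary analysis reads: "Paired t tests will be conducted between the lowest score from the post-treatment assessments and the baseline symptom levels". The scale is not named. The secondary analyses are time to relapse, imaging and blood studies. The interim paragraph then states: "The above analyses will be conducted on data from the first ten subjects to ensure that there is preliminary support for the proposed hypotheses". It does not define support, set a threshold or name a consequence.

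For the cells kept for the insulin and cytokine challenges, Section 7.3 says: "Once all samples are collected cells will be immortalized to ensure sufficient tissue availability". The two assays come after that step.

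Section 3.2 makes the primary outcome response status, a reduction of at least 50% on a CDRS formula that subtracts 17 from baseline. The exit score is "the latest CDRS score obtained on Visit 10" or at one of Visits 11-16. Section 8.5 is a general risk-benefit stop, and the Section 8.6 panel reviews safety. Neither is linked to the ten-subject look.

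**The concern.** A check on support is useful only if it can fail when there is nothing to support. The minimum of several fluctuating scores lies below a single baseline score on average, so the paired t test starts from a non-zero difference without any drug effect. A significant result at ten subjects could then be read as encouragement in an unblinded single-arm study of adolescents when it carries little information.

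The test also does not address what the interim is meant to support. The primary hypothesis in Section 2 concerns response rates and the primary endpoint is response status, whereas the t test concerns the mean of each person's best score.

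Finally, the interim paragraph takes in all the analyses above it, including two assays that the same section schedules after sample collection is complete.

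**Working it through.** No figure in the plan can be reproduced, because n=20 is given without inputs.

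**Inputs from the documents**
- Interim n = 10, final n = 20 (Sections 7.3 and 3.1).
- Post-treatment CDRS scores: one at Visit 10 (Section 6.6) plus "weekly follow-up visits for 6 weeks" (Section 6.7), so k = 1 + 6 = 7. Section 3.1 also mentions a 4-week observational period, which would give k = 1 + 4 = 5. The two lengths need reconciling; both were run.
- Primary population: completers of six infusions (Section 7.2). Eight of ten was run as a sensitivity case.

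**Assumptions, none stated in the plan**
- Two-sided 5% level; normal scores with equal means and variances at all visits (no effect, no trend).
- Correlation rho^(weeks apart), with rho from 0 to 0.95.
- Baseline one, three or four weeks before Visit 10. One week is simply equal spacing. The schedule in Section 6.8 (up to a week before treatment, two weeks of infusions, up to a week after) points to the longer gaps.

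**Statistic.** d = min(post scores) - baseline; t = mean(d) / (SD(d)/√n), counted when significant in the direction of improvement. The nominal rate is 2.5%.

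**Hand check, rho = 0, k = 7.** The mean of d is -1.35 SD. The variance of the minimum of seven is about 0.39, so SD(d) = √(1 + 0.39) = 1.18. The typical t at n=10 is -1.35/1.18 × √10 = -3.6, beyond the critical value of -2.26 on 9 df.

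**Simulation, n=10, k=7 (20,000 trials per cell, Monte Carlo error below 0.01): share showing improvement**

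| Gap to Visit 10 | rho 0 | 0.5 | 0.8 | 0.9 | 0.95 |
|---|---|---|---|---|---|
| 1 week | 0.90 | 0.84 | 0.76 | 0.71 | 0.69 |
| 3 weeks | 0.90 | 0.76 | 0.59 | 0.51 | 0.48 |
| 4 weeks | 0.90 | 0.75 | 0.55 | 0.46 | 0.41 |

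Other cases over the same grid:
- n=10, k=5: 0.29-0.78.
- n=8, k=7: 0.33-0.80.
- n=8, k=5: 0.23-0.66.
- Final n=20: 0.76-0.999 with k=7 and 0.57-0.99 with k=5.
- One fixed post-treatment visit, n=10: 0.025, as it should be.

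**Two looks with a valid test (fixed visit, n=10 then n=20)**
- Success claimable at either look, each at 5%: overall error about 8.4%.
- Continue only if p<0.05 at n=10, then test at n=20: about 1.5%.
- p<0.001 at n=10, 5% at n=20, success at either: about 5.0-5.1%.

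**Precision of a responder count at n=10 (exact 95%).** 3/10: 7-65%. 5/10: 19-81%.

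**The case against.** This is an uncontrolled pilot with a randomised placebo-controlled trial planned next (Section 5.2), so formal error control matters less than in a confirmatory study. That is fair, and it favours a descriptive look over a test.

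A reader might infer that the second look pushes the false-positive rate above 5%. The documents do not support this. The 8.4% requires that success may be claimed at either look, and no section allows that. The wording reads more like a go/no-go check, under which a valid test's error falls to about 1.5%. For the lowest-score test itself, the null rejection rate is already high at n=20, so the extra look is not the main fault.

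A reader might also infer that continued enrolment hangs on this result. No section says so. The supportable criticism is that support and its consequence are undefined.

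Nor can it be said that the check passes more often than not in every case. With rho of 0.9 or more and a four-week gap, or with fewer assessments or completers, the pass rate falls below one half. A stricter level lowers it too. It remains far above nominal in all settings tried.

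The assay clash is narrow. It does not touch the microarray, which is not described as waiting for all samples.

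**Conclusion.** The concern holds in limited form. As a screen, the interim primary test is weak: it shows improvement with no effect in about 41-90% of trials with seven CDRS assessments, and about 23-80% with five assessments or eight completers, against a nominal 2.5%. These ranges rest on an assumed two-sided 5% level, assumed correlations and an assumed spacing of baseline. The direction of the bias does not depend on those choices.

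The cause is the lowest-score contrast, so alpha spending would not repair it. Inflation of the final error by the look itself is not established, because the plan never says success may be claimed at ten subjects. The timing conflict for the insulin and cytokine assays follows from the text alone. The point should be corrected, and rewording the plan is enough.

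**What to change.** Replace the interim paragraph in Section 7.3 by one descriptive look at ten subjects that reports:
- the number of CDRS responders by the Section 3.2 formula, with Visit 10 named as the exit visit, and the exact 95% interval;
- the mean Visit 10 CDRS change with its 95% interval;
- adverse events.

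State that no efficacy claim is made at that look and what, if anything, it may change. Do not use the lowest-score test there, and leave out the insulin and cytokine assays.

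In the final primary analysis, replace the lowest score by Visit 10, keeping the completer population of Section 7.2, and state the significance level. If an interim test is still wanted, p<0.001 keeps the overall error near 5% only with this fixed-visit test. The lowest-score test at n=10 with k=7 still passes p<0.001 in about 3-25% of null trials.

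No visits, participants or procedures are added. The cost is that there are no early p-values at n=10, and a final analysis that no longer describes each person's best score. The best score can still be reported descriptively.
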